9.17. Biomarkers

9.17.1. Ethyl Glucuronide

Ethanol is excreted from the body in a variety of ways, including

- Direct excretion of ethanol (5%-10%) in urine, sweat, and breath
- Metabolic excretion by conversion to acetaldehyde or acetic acid (>90%)
- Metabolic excretion by conversion to ethyl glucuronide (EtG) and ethyl sulfate (<0.1%), both of which are readily eliminated through urination

While most of these excretory products are detectable in urine for very short periods of time (<24 hours), EtG has a longer half-life and may be detectable in urine for up to 72 hours after consumption, depending on the dose taken prior to specimen collection. Although higher amounts of EtG might indicate greater alcohol consumption, the exact EtG number is influenced by several factors, including how recently alcohol was consumed. The presence of EtG in urine indicates only that the individual was exposed to ethanol at some point in the recent past before testing, typically within the preceding 72 hours.

There are some limitations to this test. It can produce a positive test from the mere exposure to alcohol that is present in many daily-use products, e.g., mouthwashes, breath sprays, foods prepared with or flavored with alcohol, and hand sanitizers. Therefore, a positive test should be confirmed either with another test or with verification from the patient that he or she did indeed drink alcohol. However, the EtG test accurately detects a person who recently consumed alcohol 70% or more of the time. One study showed that for moderate to heavy drinking, this value increases to 85% ([Shukla, 2017](#)).

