11.2 Conventions for summary statistics and data displays

The minimum set of summary statistics for numeric variables will be: n, mean, standard deviation (SD) (or standard error), median, minimum, and maximum. 95% confidence intervals (CI) will be presented where appropriate for data interpretation.

Categorical data will be summarised in frequency tables with n and percentage. Summaries of a categorical variable will include all recorded values.

The minimum and maximum values will be presented with the same number of decimal places as the raw data collected on the case report form (CRF) (or to 3 significant figures for derived parameters less than 100 and as integers for values more than 99). The mean and percentiles (eg median) will be presented using one additional decimal place. The standard deviation and standard error will be presented using two additional decimal places.

12 Data handling conventions

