12.1 Premature withdrawal and missing data

All patients who withdraw prematurely from the study or study drug will be included in the statistical analyses.

If a patient completes the treatment period but has missing data, then this will be made apparent in the patient listings. Missing data will not be imputed.

If the study is prematurely discontinued, all available data will be listed and a review will be carried out to assess which statistical analyses are still considered appropriate.

Data collected at unscheduled time points during the study will not be used in the summaries or data analyses. They will be included in the listings.

If time information (ie hours and/or minutes) for adverse events (AEs) or concomitant medication is missing, but the day is present, then the time will be calculated in days. If date information is partial or missing, then any derived times (eg AE start time from last study medication) will be listed as missing.

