14.7 Clinical laboratory evaluations

Data from haematology, coagulation, clinical chemistry and alcohol biomarkers at each planned assessment, and changes from baseline at each planned post baseline assessment, will be summarised by treatment.

Clinically significant abnormal laboratory tests will be listed. Frequencies of clinically significant postpose abnormal laboratory tests will be summarised.

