14.2.9	Summary of Craving Visual Analogue Scale (VAS)	ITT	16.2.6.9	T_PD1
14.2.10	Summary of Clinical Global Impression of Severity (CGI-S)	ITT	16.2.6.10	T_PD6
14.2.11	Summary of Patient Global Impression of Change (PGIC)	ITT	16.2.6.11	T_PD6
14.2.12	Summary of Clinical Institute Withdrawal Assessment for Alcohol-Revised (CIWA-Ar)	ITT	16.2.6.12	T_PD1
14.2.13	Summary of Short Inventory of Problems (SIP)	ITT	16.2.6.13	T_PD2
14.3	SAFETY DATA			
14.3.1.1	Overall summary of treatment-emergent adverse events	Safety	16.2.7.1	T_AE2
14.3.1.2	Summary of treatment-emergent adverse events	Safety	16.2.7.1	T_AE1
14.3.1.3	Summary of drug-related treatment-emergent adverse events	Safety	16.2.7.1	T_AE1
14.3.1.4	Summary of treatment-emergent adverse events by maximum severity	Safety	16.2.7.1	T_AE3
14.3.1.5	Summary of treatment-emergent adverse events by day of onset	Safety	16.2.7.1	T_AE4
14.3.2.1	Listing of fatal adverse events	Safety	16.2.7.1	L_AE1_PG
14.3.2.2	Listing of non-fatal serious adverse events	Safety	16.2.7.1	L_AE1_PG
14.3.2.3	Listing of other significant adverse events	Safety	16.2.7.1	L_AE1_PG
14.3.3	Narratives of deaths, other serious and significant adverse events	Safety		-
14.3.4.1	Summary of post dose clinically significant abnormal laboratory values by treatment and planned relative time	Safety	16.2.8.1, 16.2.8.3, 16.2.8.5	T_LB4
14.3.4.2	Summary of post dose clinically significant abnormal alcohol biomarker values by treatment and planned relative time	Safety	16.2.8.7	T_LB4
14.3.5.1	Summary of chemistry laboratory values	Safety	16.4	T_LB2
14.3.5.2	Summary of haematology laboratory values	Safety	16.4	T_LB2
14.3.5.3	Summary of coagulation laboratory values	Safety	16.4	T_LB2
14.3.5.4	Summary of alcohol biomarker data	Safety	16.4	T_LB2

Table	Description	Population	Source Listing	Template (Shells below)
14.3.6.1	Summary of vital signs	Safety	16.4	T_VS1
14.3.6.2	Summary of vital signs of potential clinical importance by treatment, planned relative time and parameter	Safety	16.2.9.1	T_VS2
14.3.6.3	Summary of vital signs of potential clinical importance by parameter and treatment (excluding baseline time point)	Safety	16.2.9.1	T_VS3
14.3.6.4	Summary of post dose clinically significant vital signs	Safety	16.2.9.2	T_VS4
14.3.6.5	Summary of peak vital signs ranges by treatment, ranges and parameter – Day 0 post dose	Safety	16.2.9.3	T_VS5
14.3.6.6	Summary of peak vital signs by treatment and parameter - baseline and day 0 post dose	Safety	16.2.9.3	T_VS6

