Programming notes: For the listing of "other significant AEs" include (from ICH E3) AEs leading to withdrawal, AEs leading to dose reduction (including drug withdrawn, interrupted, reduced or similar) and AEs with AEOSE=Y. If AEOSE has not been collected then use "Otherwise significant" in the CRF.

Template L_LB1_PG

Listing 16.2.x.xx Listing of post dose clinically significant abnormal chemistry laboratory values

Treatment	Patient	Laboratory test (units)	Planned Relative Time	Date/Time	Value	Clinically Significant?
Treatment 1	1001	XXX	Time 1	01JAN2002/13:34		
			Time 2	01APR2002/09:22		Y

Programming notes: Lists only patients with clinically significant post-dose results. Alcohol biomarkers, include CDT and Urine EtG

Template L_VS1_PG

Listing 16.2.x.xx Listing of vital signs of potential clinical importance

Treatment	Patient	Planned Relative Time	Date/Time	Systolic Blood Pressure (mmHg)	Diastolic Blood Pressure (mmHg)	Etc (units)
		24 H	26SEP2012:09:57	63	148*	

* Value of potential clinical importance

Template L_VS2_PG

Listing 16.2.x.xx Listing of clinically significant vital signs

Treatment	Patient	Planned Relative Time	Date/Time	Vital Sign Finding	Comment on Clinical Significance
-----------	---------	-----------------------	-----------	--------------------	----------------------------------

Programming notes: Lists only values with abnormal CS

Template L_VS3_PG

Listing 16.2.x.xx Listing of peak vital signs data

Treatment	Patients	Planned Relative Time	Systolic Blood Pressure (mmHg)	Diastolic Blood Pressure (mmHg)	Heart Rate (beats/min)
		Predose	160	148	50
		Day 0, Postdose	163	148	55

Programming notes: Continued with all treatments and subjects. List only the maximum value

Template L_EG1_PG

Listing 16.2.x.xx Listing of QTcF values of potential clinical importance

QTcF (msec)									
Treatment	Patient	Planned	Date/Time	Heart	QRS		QRS		Change
		Relative Time		Rate	PR Int.	Dur.	Axis	QT Int.	from
				(bpm)	(msec)	(msec)	(deg)	(msec)	Observed Baseline
		24 H	26SEP2012:09:57	63	148	78	50	390	396 -6.5

* Value of potential clinical importance

Template L_EG2_PG

Listing 16.2.x.xx Listing of abnormal ECG findings

Treatment	Patient	Planned Relative Time	Date/Time	ECG Finding	Comment on Clinical Significance
-----------	---------	-----------------------	-----------	-------------	----------------------------------

Programming notes: Lists only abnormal values or values with comment on ECG result

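### Urine EtG is summarised only as a continuous level and change; the SAP plans no count of EtG-positive patients and has no below-limit rule for it

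*SAP*

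**What the plan says.** SAP 14.7 plans that "Data from haematology, coagulation, clinical chemistry and alcohol biomarkers at each planned assessment, and changes from baseline" will be summarised by treatment. In SAP 19.1 the table is 14.3.5.4, "Summary of alcohol biomarker data", built on template T_LB2, which shows n, mean, SD, median, minimum and maximum for the value and again for its change. A programming note in the listing outlines confirms that EtG belongs here: "Alcohol biomarkers, include CDT and Urine EtG". The general convention in SAP 11.2 is the same: "The minimum set of summary statistics for numeric variables will be: n, mean, standard deviation (SD) (or standard error), median, minimum, and maximum".

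The only categorical display is Table 14.3.4.2. It counts biomarker values that are post-dose and judged clinically significant, so it neither applies an EtG cut-off nor includes Screening. The endpoint in SAP 4.2.3, however, is EtG at Days 1, 28, 56 and 84 against Screening.

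Protocol 9.17.1 says what the test can show: "The presence of EtG in urine indicates only that the individual was exposed to ethanol at some point in the recent past before testing". The window it gives is usually 72 hours. On the level it says two things: "Although higher amounts of EtG might indicate greater alcohol consumption", but "the exact EtG number is influenced by several factors, including how recently alcohol was consumed". It also says that a positive should be confirmed by another test or by the patient.

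The SAP's rule for results below quantification (section 15.1) covers plasma concentrations only. SAP 12.1 says "Missing data will not be imputed".

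**The concern.** The planned summary does not match the way the protocol describes the test. The protocol presents EtG mainly as a yes/no indicator of recent exposure. The direct summary of such a test is how many of the patients tested were positive at Screening and at each later visit, and no table gives it. What is planned averages a number that depends partly on how long before the visit the last drink was taken. In a group of up to 12, that average can be carried by one patient.

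Below-limit results matter because they are what abstinence should produce. How they enter the summary decides whether the median and the mean describe all patients tested or only the positive ones, and the SAP leaves this open.

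EtG carries some weight in this study. Under the Schedule of Events it is the only alcohol biomarker at Day 56, since CDT, haematology and chemistry are next taken at Day 84. It is one of the measures of improvement in the correlation endpoint. The endpoint for percentage of abstinent days calls for biomarker verification, for which positive/negative status is the natural input, although the SAP Appendix A calculation does not mention it.

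**Working it through.** The plan states no EtG value, unit, cut-off or variability, so there is no figure of its own to reproduce. The levels below are assumed and shown as a range.

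**Inputs from the documents.** Up to 12 patients in up to 2 cohorts (SAP 5). EtG at Screening and Days 1, 28, 56 and 84 (Protocol Table 1). Screening is the only pre-dose EtG, so under SAP 12.2 baseline is the Screening value.

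**When one patient reverses the mean change.** With n patients, of whom n − 1 fall by an average of d and one rises by r:

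mean change = (r − (n − 1) × d) / n, which is positive only if r > (n − 1) × d.

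At n = 12 the rise must exceed 11 times the others' average fall. At n = 6, as could occur if two cohorts are summarised separately, it must exceed 5 times.

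**Worked examples, n = 12.** All start at the same level, eleven fall to 0 and the twelfth rises.

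| Screening level | Twelfth patient later | Mean change | Median change |
|---|---|---|---|
| 500 | 10,000 | (9,500 − 5,500)/12 = +333 | −500 |
| 2,000 | 10,000 | (8,000 − 22,000)/12 = −1,167 | −2,000 |
| 2,000 | 30,000 | (28,000 − 22,000)/12 = +500 | −2,000 |
| 5,000 | 50,000 | (45,000 − 55,000)/12 = −833 | −5,000 |
| 5,000 | 80,000 | (75,000 − 55,000)/12 = +1,667 | −5,000 |
| 5,000 | 100,000 | (95,000 − 55,000)/12 = +3,333 | −5,000 |

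In every row the positives go from 12/12 to 1/12 = 8% (exact 95% CI 0.2% to 38%), however high the one positive value is. From a level of 5,000, the twelfth patient must rise by more than 55,000, that is to above 60,000, before the mean change turns positive.

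**How often, under assumptions.** A simulation used 12 patients and 100,000 runs per setting. The level was zero if negative and lognormal if positive (log-SD 0.5 to 2.5), and independent between time points. The mean rose although fewer patients were positive in:
- 0.0% to 6.2% of runs when the probability of a positive fell from 90% to 10%
- 0.1% to 13.7% for 100% to 25%
- 1.3% to 19.1% for 75% to 25%
- 7.7% to 28.8% for 75% to 50%

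The higher figures belong to the more skewed levels. In the 75% to 25% setting, most of these reversals came from one patient: removing the largest change restored a fall in 1.2% to 15.5% of all runs.

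**Below-limit results.** Take the 80,000 row. If the eleven undetectable results are kept at 0, the visit shows n = 12, mean 80,000/12 = 6,667, median 0 and maximum 80,000. If they were left out, it would show n = 1 with mean and median both 80,000. The protection from the median therefore depends on the missing rule.

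**The case against.** The strongest reply is that the mean is not the whole result. T_LB2 also gives median, minimum and maximum, and complete listings of all data are produced. In a group of 12, an outlier would be seen. This stands as long as below-limit results are kept.

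A reader might infer three stronger things that the documents do not support.
- *That one recent heavy drinker will reverse the group result.* Reversal needs a rise above 11 times the others' average fall at n = 12, and the median change stayed negative in every worked example. How likely it is depends on EtG values that the documents do not give.
- *That the protocol calls the level uninterpretable, so the numeric summary should go.* In "The presence of EtG in urine indicates only that the individual was exposed to ethanol at some point in the recent past before testing" the word only qualifies the presence of EtG. The same section allows that "Although higher amounts of EtG might indicate greater alcohol consumption".
- *That abstinent patients will drop out of the mean.* Nothing says how the laboratory reports or stores a below-limit result. Such a result is not missing, so "Missing data will not be imputed" does not by itself remove it. Dropping out is a risk that the SAP fails to exclude, not something it prescribes.

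It can also be said that a percentage positive has limits of its own. It covers about 72 hours before each visit, not the whole follow-up, and 9.17.1 warns that everyday products containing alcohol can produce a positive. That is fair. It argues for adding the count beside the level and noting confirmation, not for omitting the count. CDT at Days 28 and 84, and MCV, ALT, AST and GGT, are also used to watch for relapse, so EtG stands alone among the biomarkers only at Day 56 and for very recent drinking.

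**Conclusion.** The gap is real and modest. The SAP summarises urine EtG only as a continuous level and change. It has no cut-off, no count of positive patients with Screening as comparator, and no below-limit rule for urine. These are facts of the text and need no assumption.

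The effect on the mean is conditional. With at most 12 patients one high value can dominate it, but reversal is possible rather than expected: about 0% to 29% of runs at n = 12 under the assumed positivity rates and lognormal levels. The planned median would still show a clear fall of the kind in the worked examples, if below-limit results are kept.

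The endpoint is exploratory, there is no hypothesis test, and drinking is measured mainly by the TLFB, so no error rate or sample size is affected. The priority is low to moderate.

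**What to change.** Before database lock:

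- Add to Table 14.3.5.4 the number and percentage EtG-positive at the laboratory's cut-off, at Screening and Days 1, 28, 56 and 84, with patients tested as the denominator. Name the cut-off.
- Add a Screening-to-visit shift table. Inclusion criterion 5 lets a patient be screened up to 14 days after the last heavy drinking day or after detoxification, which is beyond the 72-hour window. Some patients may therefore already be negative at Screening, and a shift table shows who they are.
- State that a below-limit urine EtG result counts as negative and stays in the numeric summary at a stated value.
- Keep the level as median and range, with individual values listed.
- Add a footnote that a positive reflects only about 72 hours and, under Protocol 9.17.1, should be confirmed by another test or by the patient.

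The cost is one extra table shell and a few sentences. The data are already collected, and CDT can stay as planned.

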14.8 Other safety measures

14.8.1 Vital signs

Vital signs at each planned assessment, and change in vital signs from baseline at each planned post baseline assessment, will be summarised by actual treatment.

Plots of individual systolic blood pressure, diastolic blood pressure, and pulse rate against time will be presented for both absolute values and change from baseline by actual treatment.

Vital signs data of PCI will be listed and summarised.

A separate listing of vital sign findings, classified as clinically significant by the investigator will also be provided. Frequency of clinically significant vital signs will be summarised.

The peak (maximum value across all time points for each patient) vital signs (systolic and diastolic blood pressure, and heart rate) at baseline and post dose on day 0 will be listed and summarised.

In addition, the number of patients will be summarised for peak post dose Day 0 under the following categories:

Systolic blood pressure (mmHg)	Diastolic blood pressure (mmHg)	Heart Rate (bpm)
< 130	< 80	<40
130 - 139	80 - 89	40 – 49
140 - 149	90 - 99	50 – 59
150 – 159	100 – 109	60 – 69
160 – 169	110 – 119	70 – 79

170 – 179	120 – 129	80 – 89
180 – 189	130 – 139	90 – 99
190 – 199	>= 140	100 – 109
200 – 209		110 – 119
210 – 219		>120
>= 220		

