4. Vital signs (HR, BP, and temperature) at baseline will be measured in triplicate within 30 min (+/- 5mins) before dosing (Triplicate measurements should be obtained as closely as possible in succession, and no more than 2 min apart (temperature does not need to be repeated in triplicate). Predose BP must be within normal range pre dose on dosing day and if not repeated ~ 1 h later. If still not in range then it is considered a Screen fail. Vital signs also to be taken in triplicate within 30 min (+/- 5mins) before dosing Then single measurements at 10, 20, 30, 40 & 60 mins, and then every 30 min (+/- 5mins) until 4 h postdose; and when the patient is assessed as ready to be discharged on Day 0, if later than 4h postdose (as per the readiness for discharge questionnaire). Vital signs from 90 min post-dose onwards will form part of the readiness for discharge questionnaire. A note should be taken of any movement of the participant during Blood Pressure measurements. If systolic Blood pressure is > 160 mmHg then repeat the Blood Pressure measurement.
5. Pregnancy tests will only be done in women of childbearing potential. Urine pregnancy tests in women of childbearing potential will be done only at Screening and before dosing on Day 0. Serum FSH tests in postmenopausal women will be done at Screening only.
6. Including previous abstinence attempts.
7. ECG to be performed in triplicate at Screening (2 minutes apart), single at other visits.
8. A physician will examine the nostrils for any evidence of irritation or reaction after dosing with BPL-003.
9. EDI & MEQ30 To be completed after the qualitative interview, if done.
10. Readiness for discharge assessment to be completed every 30 minutes (+/- 5mins) starting 90 minutes after dosing before discharge from clinic up to 4 hours post dose. If the patient is not ready for discharge at 4 hours post dose then the questionnaire will be repeated again at the point Investigator believes patient may be ready for discharge.
11. The Psychedelic Integration Visit should be held in the clinic but may be done via video call at the discretion of the Investigator or for logistical reasons. The psychedelic integration on Days 1 and 7 should be started after all questionnaires/scales have been completed.
12. See Section 9.7.

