12.2 Derived and transformed data

Baseline will be considered to be the latest value obtained before study drug administration (eg before dosing on Day 0, or Screening if not recorded at predose on Day 0 or Day -3).

Laboratory data will be reported in standard units. Out-of-range laboratory tests may be repeated. If a test is out-of-range at baseline and repeated before dosing, the latest repeat value before dosing will be used as baseline. However, if a test is out-of-range and repeated at any other time during the study, the out-of-range value (not the repeat value) will be included in statistical summaries.

Triplicate electrocardiogram (ECG) measurements will be taken on screening and the mean of the 3 measurements will be used for analysis. Triplicate vital sign measurements at baseline and the mean of the 3 measurements will be used for analysis.

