Table 14.3.6.xx Summary of vital signs of potential clinical importance by parameter and treatment (excluding baseline time point)

Treatment	Systolic Blood Pressure (mmHg)		Diastolic Blood Pressure (mmHg)		Heart Rate (beats/min)		Temperature (C)		etc		Overall*	
	n	(%)	n	(%)	n	(%)	n	(%)	n	(%)	n	(%)
Treatment 1 (N=xx)												

Source: Listing 16.2.xx

Patients only counted once per parameter

*Patients only counted once per treatment

Programming notes: Continued with all parameters. n = total number of results for that parameter
Only include post-treatment time points

Template T_VS4

Table 14.3.6.xx Summary of post dose clinically significant vital signs

Treatment	Planned Relative Time	Clinically Significant	
		n	(%)
Treatment 1 (N=xx)	Time 1 Time 2		

Programming notes: Continued with all timepoints. n = total number of results for that parameter

Template T_VS5

Table 14.3.7.xx Summary of peak Vital Signs ranges by treatment, ranges and parameter - Day 0 post dose

	Systolic Blood Pressure (mm Hg)										
	<130	130 - 139	140 – 149	150 – 159	160 – 169 n	170 – 179	180 – 189	190 – 199	200 - 209	210 – 219	> =220
Treatment	n (%)	n (%)	n (%)	n (%)	(%)	n (%)	n (%)	n (%)	n (%)	n (%)	n (%)
Treatment 1 (N=xx)											

Source: Listing 16.2.xx

The maximum value across all time points per subject is used for analysis.

Programming notes: Continued with all variables . n = total number of results for that parameter.
Continued with all the ranges in **section 14.8.1**

Template T_VS6

Table 14.3.6.xx Summary of peak vital signs by treatment and parameter - baseline and Day 0 post dose

Variable (units)	Treatment	Planned Relative Time	n	Mean	SD	Median	Min	Max
Systolic Blood Pressure (mmHg)	Treatment 1 (N=xx)	Predose Day 0, Postdose						

Source: Listing 16.2.xx

Programming notes: Continued with DBP and HR. The maximum value across all time points per subject are used for analysis.

Template T_EG2

Table 14.3.7.xx Summary of ECG values

Variable (units)	Treatment	Planned Relative							Change from Baseline					
		Time	n	Mean	SD	Median	Min	Max	n	Mean	SD	Median	Min	Max
Heart Rate (bpm)	Treatment 1 (N=xx)													
PR Interval (msec)	Treatment 1 (N=xx)													

Source: Listing 16.2.xx

Programming notes: Continued with all time points
Do not summarise RR or QRS axis

Template T_EG3

Table 14.3.7.xx Summary of QTcF values and changes in QTcF values of potential clinical importance

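### The SAP's peak vital-sign display sets a maximum of up to 11 post-dose readings beside a value from one pre-dose triplicate, and does not settle whether that value is a maximum or a mean

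*SAP*

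**What the plan says.** SAP 14.8.1 names the quantity as "The peak (maximum value across all time points for each patient) vital signs" and says that for systolic pressure, diastolic pressure and heart rate the values "at baseline and post dose on day 0 will be listed and summarised". The matching shell in SAP 19.2.1 is T_VS6, titled "Summary of peak vital signs by treatment and parameter - baseline and Day 0 post dose". It has a Predose row and a Day 0 Postdose row, each with n, mean, SD, median, minimum and maximum. Its programming note reads "The maximum value across all time points per subject are used for analysis". Listing L_VS3 shows the same two rows for each patient, with the note "List only the maximum value".

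SAP 12.2 gives a different rule for the pre-dose value: "Triplicate vital sign measurements at baseline and the mean of the 3 measurements will be used for analysis". No sentence says which rule governs the peak display.

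The reading counts come from the protocol. Section 10.1.2 and Table 1 note 4 set one triplicate before dosing, with readings at most 2 min apart. After dosing, note 4 specifies "Then single measurements at 10, 20, 30, 40 & 60 mins, and then every 30 min (+/- 5mins) until 4 h postdose". Section 10.1.2 adds that the readings from 90 min onwards may end once the patient is confirmed ready for discharge, and that a systolic reading above 160 mmHg is repeated. The SAP does not adjust for the unequal counts or footnote them.

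**The concern.** The expected maximum of a set of readings rises with the size of the set. A peak drawn from 11 readings will tend to exceed one drawn from three even if nothing has changed, and it will exceed a mean of three by more still. T_VS6 invites exactly that before-and-after comparison. The study is open label with no placebo group, so the Predose row is the only reference in the table. Tachycardia and raised blood pressure are named risks in protocol section 1.6, and a reader will want to know how far the peak moved. As specified, the display mixes any real movement with a counting artefact of unknown share. Two programmers following different sections of the SAP could also produce different Predose rows.

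**Working it through.** The documents state no figure for this comparison, so there is none to reproduce.

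**Reading counts**
- Post dose, planned: 10, 20, 30, 40, 60, 90, 120, 150, 180, 210 and 240 min, so m = 11.
- Post dose, if the patient is ready at the first discharge check (90 min) and readings stop: 10, 20, 30, 40, 60 and 90 min, so m = 6.
- Pre dose: k = 3.

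**Chance of a higher post-dose value with no drug effect**
- Against the maximum of three: if the readings are exchangeable, the largest of all m + k is equally likely to be any of them, so P = m/(m + k), whatever the distribution. For m = 11, 11/14 = 0.786. For m = 6, 6/9 = 0.667.
- Against the mean of three, with independent normal readings: P is the integral of [1 − Φ(x)^m] over the N(0, 1/3) density. This gives 0.978 for m = 11 and 0.933 for m = 6.

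**Expected gap, in within-patient SDs**
- Normal order statistics: E[max of 3] = 0.846, E[max of 6] = 1.267, E[max of 11] = 1.586.
- For m = 11: 1.586 − 0.846 = 0.74 against the maximum, and 1.59 against the mean.
- For m = 6: 1.267 − 0.846 = 0.42 against the maximum, and 1.27 against the mean.

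| Post-dose readings | Pre-dose value | P(post > pre) | Gap (SD) | Gap if SD is 5-10 mmHg |
|---|---|---|---|---|
| 11 | maximum of 3 | 79% | 0.74 | 3.7-7.4 mmHg |
| 11 | mean of 3 | 98% | 1.59 | 7.9-15.9 mmHg |
| 6 | maximum of 3 | 67% | 0.42 | 2.1-4.2 mmHg |
| 6 | mean of 3 | 93% | 1.27 | 6.3-12.7 mmHg |

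The documents give no within-patient SD. The 5-10 mmHg range is an assumption, and the last column scales with it.

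**Sensitivity**
- Serial correlation (simulation, 200,000 runs per setting; 0-90% of within-patient variance autocorrelated, time constant 10-120 min): with 11 readings, 79-85% against the maximum and 92-98% against the mean. With six readings, 67-75% and 84-93%.
- Rounding independent readings to whole mmHg at an SD of 5 or 8 mmHg gives 76-77% for 11 readings against the maximum of three.
- At 12 patients, 12 × 11/14 = 9.4 would be expected to show a higher post-dose peak against the maximum of three.

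**Equal counts**
- Three against three gives 3/6 = 50% for exchangeable readings. Taking the 10, 20 and 30 min readings against the triplicate over the same correlation settings gives 50-59%, with a gap of at most 0.26 SD. The residue arises because the triplicate readings lie closer together in time.

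**The case against.** The strongest reply is that little rests on this table. T_VS6 has no change column, no count of patients who rise and no test, and the SAP tests no hypotheses. The primary vital-sign endpoint is the share of patients with post-dose values judged clinically significant, reported through T_VS4. Change from baseline at each time point (T_VS1) and the individual plots show the time course without comparing maxima, and T_VS5 categorises the post-dose peak on its own. All of this stands, and it limits the point to one supplementary table and its listing.

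The reading count is also not fixed at 11, and with six readings the artefact is smaller. That stands, and it is a further reason to print the count. Exchangeability is an idealisation too: pre-dose pressure must be in range before dosing, and the triplicate spans minutes while post-dose readings span hours. The percentages are therefore reference values, not predictions.

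It can further be said that the bias overstates a rise, which is the cautious direction for safety, and that restricting the peak to an early window would hide later peaks. The second part is right, so the full peak should stay. The first does not justify an unlabelled comparison.

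A reader might infer that the plan will report a rise in about 80% of patients, or that any rise shown is spurious. The documents support neither. No such percentage is tabulated; it could only be counted from the paired rows of L_VS3, and 79% belongs to the maximum-of-three rule alone. Since raised pressure and heart rate are expected risks, part of an observed gap may well be real.

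**Conclusion.** The point holds for the peak table and listing. In the absence of any drug effect, the post-dose row is expected to exceed the pre-dose row by 0.74 within-patient SD if the pre-dose value is the maximum of three, and by 1.59 SD if it is the mean. These gaps assume 11 independent, normally distributed post-dose readings with the same mean and variance as the pre-dose readings; early stopping reduces them. The mmHg values also rest on the assumed SD.

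Separately, and without any assumption, SAP 12.2 and 14.8.1 give different rules for the pre-dose value, and the choice roughly doubles the artefact. The inference that the primary safety endpoint is biased is not supported, because that endpoint does not use this comparison. The change is worth making because it is cheap and the display concerns a named risk with no control group.

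**What to change.** 1. In SAP 12.2 and 14.8.1, state that the pre-dose peak is the maximum of the individual triplicate readings, and that the mean of three remains the baseline for change-from-baseline summaries.
2. Keep the all-readings post-dose peak in T_VS6 and L_VS3. Show the number of readings behind each peak, and footnote that peaks from unequal numbers of readings are not directly comparable.
3. Add a paired row with equal counts, for example the maximum of the 10, 20 and 30 min readings against the maximum of the triplicate, with the within-patient change.
4. State whether repeats taken after a systolic reading above 160 mmHg enter the peak. SAP 12.1 leaves unscheduled time points out of summaries but does not say whether a repeat at a planned time is one of them.

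The cost is SAP wording, one extra row in T_VS6 and small additions to L_VS3, with no new measurements. The equal-count row does not cover peaks after 30 min; these stay visible in the all-readings row, T_VS1 and T_VS5.
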